## 5.3 Schematic diagram

A study schematic is presented in [Figure 5-1](#).

**Figure 5-1: Schematic diagram**

FV=Final Visit; Ig=immunoglobulin; OLE=open-label extension; PEOT=premature end of treatment; sc=subcutaneous; SOC=standard of care; V=Visit

See [Table 8-1](#) for details on the management of the Observation and Stabilization Periods.

## 5.4 Rationale for study design and selection of dose

### 5.4.1 Pathophysiology of CIDP

Production of pathogenic auto-antibodies is a major feature of a number of autoimmune diseases often associated with a specific pathomechanism. Cellular and humoral immune mechanisms are thought to be involved in the pathogenesis of CIDP resulting in inflammatory lesions in the spinal roots, proximal nerve trunks, and along the peripheral nerves. The essential role of the autoimmune antibodies in mediating this pathology is supported by the improvement seen after PLEX and IA. Identification of the specific antigenic target(s) of the autoimmune antibodies in CIDP is expanding with recent immunological techniques. Treatments aimed at reducing the quantity of circulating IgG auto-antibodies are being used for primary and secondary therapy of autoimmune diseases, particularly where corticosteroid-based immune suppression is not or no longer effective. The therapeutic approach of these treatments is based on lowering levels of pathogenic auto-antibodies, which represents rational and effective treatment modalities of autoimmune diseases.

#### **5.4.2 Mechanism of action of rozanolixizumab**

Rozanolixizumab is a humanized IgG4 monoclonal antibody that is being developed as an inhibitor of the activity of FcRn. The FcRn recycles IgG and albumin and transports it bidirectionally across epithelial barriers. Recent studies have shown that FcRn rescues both IgG and albumin from intracellular lysosomal degradation by recycling it from the sorting endosome to the cell surface (Anderson et al, 2006). Rozanolixizumab has been specifically designed to block IgG binding to FcRn without blocking the binding and recycling of albumin. By blocking the activity of FcRn, rozanolixizumab accelerates the catabolism of IgG antibodies, including IgG auto-antibodies. The aim is to reduce the concentration of pathogenic IgG in patients with autoimmune diseases mediated by the action of IgG auto-antibodies.

#### **5.4.3 Choice of study design and endpoints**

The primary objective of the study is to evaluate the clinical efficacy of rozanolixizumab as a treatment for subjects with CIDP. This 2-arm parallel design study will compare the change from Baseline to Week 13 (Day 85) in iRODS score in the rozanolixizumab compared to placebo treatment groups as the primary efficacy variable. In addition, the study will evaluate efficacy using CIDP relapse up to Week 13 (Day 85) after treatment start according to the iRODS, adjusted INCAT scores, and maximum grip strength as assessed by site personnel, as well as treatment comparison versus placebo for the rozanolixizumab group. Both the iRODS and INCAT are measures of disability in CIDP. The INCAT scale was used in the registration study for IGIV-C (Gamunex-C; Hughes et al, 2008). The iRODS has demonstrated significantly higher responsiveness to the ordinal-based INCAT-Overall Neuropathy Limitation scale (INCAT-ONLS) and the modified INCAT sensory scale when using the minimum clinically important differences using the obtained individual standard error (MCID-SE) method for defining a relapse ( $MCID-SE \leq -1.96$ ) (Vanhoutte et al, 2015; Draak et al, 2014). The randomized, placebo-controlled study design is widely accepted as optimal for assessing efficacy. Grip strength was assessed in the CIDP ICE (Merkies et al, 2010) and the PATH trials (van Schaik et al, 2017) and 14kPa was evaluated to be the MCID for determining a relapse.

A treatment duration of 11 weeks was judged to be sufficiently long to evaluate a difference between rozanolixizumab [REDACTED] treatment and placebo (Nobile-Orazio et al, 2015; Hughes et al, 2008).

#### **5.4.4 Rationale for dose selection**

The dose and regimen of IMP to be used in the current study (rozanolixizumab [REDACTED] sc) was selected based on the results from first-in-human study UP0018, alongside the emerging safety data from the MG and ITP studies (MG0002 and TP0001).

UP0018 was a randomized, subject-blind, investigator-blind, placebo-controlled, single dose-escalating study to evaluate the safety and PK and to explore the PD of rozanolixizumab doses of [REDACTED] in 49 healthy male and female subjects. Data indicate that mean absolute decreases in IgG and mean percent change from Baseline IgG were greater in the active dose groups (n=6 each) compared to the pooled iv and sc placebo group (n=12) with maximum decreases of 49.3% (range: 44.6% to 55.9%) observed on Day 6 for a rozanolixizumab [REDACTED] iv dose and 42.8% (range: 39.6% to 48.6%) on Day 9 for a rozanolixizumab [REDACTED] sc dose. Rozanolixizumab was tolerated with an acceptable

safety profile after the single administration of a [REDACTED] sc dose, and all subject-reported TEAEs had a maximum intensity of mild or moderate.

MG0002 is a completed, Phase 2, multicenter, randomized, investigator- and subject-blind, placebo-controlled, 2-arm repeat dose, treatment sequence study evaluating the safety and efficacy of rozanolixizumab sc [REDACTED] in 43 subjects with generalized MG.

[REDACTED]

[REDACTED]

[REDACTED]

[REDACTED]

[REDACTED]

[REDACTED] Overall, repeated administrations of rozanolixizumab at dose levels of [REDACTED] sc were generally [REDACTED] and well tolerated, with an acceptable safety profile. No new safety concerns were identified; a summary of results is included in the IB.

TP0001 is a completed, Phase 2, multicenter, open-label, multiple-arm study to evaluate the safety, tolerability, and efficacy of rozanolixizumab in subjects with primary persistent or chronic ITP. The following dose arms were used in the study:

- Dose Arm 1 (15 subjects): rozanolixizumab [REDACTED]
  - Dose Arm 2 (15 subjects): rozanolixizumab [REDACTED]
  - Dose Arm 3 (12 subjects): rozanolixizumab [REDACTED]
  - Dose Arm 4 (12 subjects): rozanolixizumab [REDACTED]
  - Dose Arm 5 (12 subjects): rozanolixizumab [REDACTED]
- [REDACTED]
- [REDACTED]

dose was well-tolerated, and a summary of the safety results is included in the IB. However, it should be noted that the exposure of rozanolixizumab was lower in subjects with ITP than subjects with MG when dosed with the same dose level.

The dose-exposure-response relationship, with total IgG as the primary endpoint, was determined using non-linear mixed effects modeling of the data from UP0018. The derived population PK-PD (structural PK-PD model based on that of Lowe [Lowe et al, 2010]) was then used to guide, through simulation, the selection of appropriate repeat dose regimens that would mimic decreases achieved by plasmapheresis paradigms and result in an IgG reduction of 70% or greater. The model-based simulations demonstrate that the chosen dose regimen of [REDACTED] sc administered weekly for a total of 12 doses are expected to produce maximum mean IgG reductions of >70% over the Treatment Period. Based on simulations, it is expected that these IgG reductions will be reached rapidly and maintained consistently with the selected dosing regimen.

This study will utilize the same liquid formulation at [REDACTED] as was used in the first in human study. In the first in human study, individual dose was achieved by diluting the formulation prior to administration. Based on the heaviest subject (81kg) at the highest sc dose [REDACTED], the maximum concentration given was [REDACTED]. This change in concentration is not predicted to have an impact on local tolerability, however to allow this to be fully assessed

the first two infusions in each subject will be given at a slower rate of approximately [REDACTED]. If no tolerability concerns are identified subsequent infusions may be given at rates up to [REDACTED].

#### **5.4.5 Justification for additional genomic analysis**

CIDP is a significantly disabling disorder. However, evidence for genetic predisposition to disease or to response to therapy is limited. No genome wide association studies have been completed and unusually for an immune mediated disease, no clear human leukocyte antigen association demonstrated. Although reports of genetic findings associated with disease or response to therapy are scarce, the role of undiscovered gene variants in pathways relating to immune system biology or peripheral nerve function cannot be ruled out. As genome wide analysis of CIDP patients becomes feasible and affordable, a clearer understanding of the role of genetic and genomic factors in CIDP biology is likely to be forthcoming.

Through the collection of whole blood, DNA analysis will help facilitate identification and characterization of genetic and/or epigenetic components of CIDP and will lead to important clues into the pathogenesis of disease and possibly advance understanding of drug response phenotypes.

Gene transcription signatures associated with CIDP biology and response of CIDP patients to IVIg therapy have been generated from whole blood messenger RNA (mRNA) microarray analysis. Such profiles may provide molecular insight into disease biology and activity and can facilitate patient stratification via gene expression panels predictive of therapeutic response and clinical outcomes.

MicroRNAs (miRNAs) are short (19-25 nucleotides) evolutionarily conserved single-stranded RNA molecules that regulate the expression of genes involved in diverse biological processes. The effect of miRNA on mRNA is mediated through the binding of the miRNA to the target mRNA ribonucleoprotein complex resulting in altered expression and decreased protein translation.

Collection of blood for analysis of RNA, proteins, and metabolites will facilitate insight into the molecular etiology of CIDP at the genomic level and may enable identification of candidate markers for treatment effect and safety, and assessment of the feasibility of patient stratification.

In summary, the DNA, RNA, proteins, and metabolites elements of CIDP require further elucidation to understand the cause, progression, and appropriate treatment of CIDP. Through the collection of blood DNA, RNA, serum, and plasma samples, these analyses will help enable further investigation of this complex disease.

## **6 SELECTION AND WITHDRAWAL OF SUBJECTS**

### **6.1 Inclusion criteria**

To be eligible to participate in this study, all of the following criteria must be met:

1. An Institutional Review Board (IRB)/Independent Ethics Committee (IEC) approved written Informed Consent form is signed and dated by the subject.
2. The subject is considered reliable and capable of adhering to the protocol visit schedule, or medication intake according to the judgment of the investigator.
3. Subject is  $\geq 18$  years of age at Visit 1 (Screening).

4. Subject has a documented definite or probable diagnosis of CIDP according to the EFNS/PNS criteria 2010.
5. Subject has an Ig-dependency confirmed by clinical examination during therapy or upon interruption or reduction of therapy within 18 months prior to Screening and documented in medical history (ie, that a decrease or withdrawal of immunoglobulin was attempted that resulted in a clinically relevant decrease in function).
6. Subject is on a stable dosage (not more than  $\pm 20\%$  deviation) for SC Ig or IV Ig and a fixed interval for at least 4 months of either treatment, eg, once weekly  $\pm 2$  days for SC Ig or every 2 to 6 weeks  $\pm 5$  days IV Ig, respectively, for stability in functioning between dosing.
7. Female subjects of childbearing potential must have a negative serum pregnancy test at the Screening Visit, which is confirmed to be negative by urine testing prior to the first dose of IMP at Week 1 (Visit 2) and prior to further dosing at each study visit thereafter.

Female subjects of childbearing potential must agree to use a highly effective method of birth control, during the study and for a period of 3 months after their final dose of IMP. Highly effective forms of birth control are methods which achieve a failure rate of less than 1% per year when used consistently and correctly. According to the International Council for Harmonisation (ICH) M3 R2, highly effective methods of birth control include:

- Combined (estrogen- and progesterone-containing) hormonal contraception (oral, implant, injectable) associated with inhibition of ovulation (which must be stable for at least 1 full month prior to Screening [Visit 1], and should remain stable during the study).
- Progesterone-only hormonal contraceptives (oral, implant, injectable) associated with inhibition of ovulation (which must be stable for at least 1 full month prior to Screening [Visit 1], and should remain stable during the study).
- Progesterone-releasing intrauterine systems or the TCu 380A intrauterine device.
- Vasectomized partner (provided sole partner and partner has medical proof of surgical success).
- True heterosexual sexual abstinence is an acceptable form of contraception when this is in line with the preferred and usual lifestyle of the person. Periodic abstinence (eg, calendar, ovulation, symptothermal, postovulation methods), declaration of abstinence for the duration of the study, and withdrawal are not acceptable methods of contraception.

Women not agreeing to use birth control must be of nonchildbearing potential, defined as being:

- Postmenopausal (for at least 2 years before the Screening Visit), verified by serum follicle-stimulating hormone level  $>40\text{mIU}/\text{mL}$  at the Screening Visit, or
- Permanently sterilized (eg, bilateral tubal occlusion, hysterectomy, bilateral salpingectomy), or
- Congenitally sterile

- 
8. Male subjects with a partner of childbearing potential must be willing to use a condom when sexually active during the study and for 3 months after the final administration of IMP. In addition, the female partner of childbearing potential of a male subject must be willing to use a highly effective method of contraception (as above), during the study period and for 3 months after the final administration of IMP. Sperm donation is not permitted during the study and for 3 months after final administration of IMP.

## **6.2 Exclusion criteria**

### **6.2.1 Exclusion criteria related to study participation**

Subjects are not permitted to enroll in the study if any of the following criteria are met:

1. Subject has previously received treatment in this study or subject has previously been exposed to rozanolixizumab.
2. Subject has participated in another study of an IMP (or a medical device) within the previous 30 days of Screening Visit or is currently participating in another study of an IMP (or a medical device). For experimental biological agents refer to Exclusion Criterion 26.

### **6.2.2 Exclusion criteria related to CIDP diagnosis**

3. Subject has a current diagnosis or has a history of Type 1 or Type 2 diabetes mellitus and/or hemoglobin A1c level >6.0%.
4. Subject with IgM paraproteinemia.
5. Subjects with known IgM-mediated neuropathy (eg, multifocal motor neuropathy).
6. Clinical or known evidence of associated systemic diseases that might cause neuropathy, including but not limited to connective tissue disease, Lyme disease, Castleman's disease and systemic lupus erythematosus, malignant plasma cell dysplasia, or treatment with agents that might lead to neuropathy (eg, amiodarone therapy).
7. Subjects on an average dose less than 0.4g IgG/kg/month over the past 4 months.

### **6.2.3 Exclusion criteria related to health status/safety of the subject**

8. Female subject who is pregnant or lactating.
9. Subject has any medical (acute or chronic illness) or psychiatric condition that, in the opinion of the investigator, could harm the subject or would compromise the subject's ability to participate in this study.
10. Subject has 12-lead ECG with abnormalities considered to be clinically significant upon medical review.
11. Subject has renal impairment, defined as:
  - Serum creatinine level of  $\geq 1.4\text{mg/dL}$  for females and  $\geq 1.5\text{mg/dL}$  for males at Screening Visit.
12. Subject has an absolute neutrophil count  $< 1500/\text{mm}^3$  ( $1.5 \times 10^9/\text{L}$ ).

13. Subject has  $>2\times$  upper limit of normal (ULN) of any of the following: alanine aminotransferase (ALT), aspartate aminotransferase (AST), or alkaline phosphatase (ALP), or  $>\text{ULN}$  total bilirubin ( $\geq 1.5\times \text{ULN}$  total bilirubin if known Gilbert's syndrome). If subject has elevations only in total bilirubin that are  $>\text{ULN}$  and  $<1.5\times \text{ULN}$ , fractionate bilirubin to identify possible undiagnosed Gilbert's syndrome (ie, direct bilirubin  $<35\%$ ).

For randomized subjects with a Baseline result  $>\text{ULN}$  for ALT, AST, ALP, or total bilirubin, a Baseline diagnosis and/or the cause of any clinically meaningful elevation must be understood and recorded in the electronic Case Report form (eCRF).

If subject has  $>\text{ULN}$  ALT, AST, or ALP that does not meet the exclusion limit at Screening, repeat the tests, if possible, prior to dosing to ensure there is no further ongoing clinically relevant increase. In case of a clinically relevant increase, inclusion of the subject must be discussed with the Medical Monitor.

Tests that result in ALT, AST, or ALP up to 25% above the exclusion limit may be repeated once for confirmation. This includes rescreening.

14. Subject has a history of alcohol use disorder or other substance use disorder (as per Diagnostic and Statistical Manual of Mental Disorders-5 [American Psychiatric Association, 2013]) within 12 months of Screening Visit.
15. Subject has a history of clinically relevant ongoing chronic infections including but not limited to human immunodeficiency virus (HIV), hepatitis B, hepatitis C, or is tested positive for HIV (anti-HIV1 or anti-HIV2 antibodies), hepatitis B (HBsAg positive or HBcAb positive without positive HBsAb), or hepatitis C antibody (HCAb) at the Screening Visit.
16. Subjects with known TB infection, at high risk of acquiring TB infection, or latent tuberculosis infection (LTBI), or current/history of nontuberculosis mycobacteria (NTMB) are excluded.
  - a. Known TB infection whether present or past is defined as:
    - Active TB infection or clinical signs and symptoms suggestive of TB (pulmonary or extrapulmonary).
    - History of active TB infection involving any organ system or findings in other organ systems consistent with TB infection.
    - Any historical evidence by radiography or other imaging modalities consistent with previously active TB infection.
  - b. High risk of acquiring TB infection is defined as:
    - Known exposure to another person with active TB infection within the 3 months prior to Screening.
    - Time spent in a healthcare delivery setting or institution where individuals infected with TB are housed and where the risk of transmission of infection is high.
  - c. LTBI (see Section 12.3 for further details and instructions).

- 
- d. NTMB is defined as a group of lung infections caused by mycobacteria different from mycobacterium tuberculosis infections.
  - 17. Subject has a family history of primary immunodeficiency.
  - 18. Subject has a clinically relevant active infection (eg, sepsis, pneumonia, abscess) or has had a serious infection (resulting in hospitalization or requiring parenteral antibiotic treatment) within 6 weeks prior to the first dose of IMP.
  - 19. Subject has active neoplastic disease or history of neoplastic disease within 5 years of Screening Visit (except for basal or squamous cell carcinoma of the skin or carcinoma in situ of the uterine cervix which has been definitively treated with SOC approaches).
  - 20. Subject has a lifetime history of suicide attempt (including an active attempt, interrupted attempt, or aborted attempt), or has suicidal ideation in the past 6 months as indicated by a “yes” answer to numbers 4 or 5 on the screening Columbia Suicide Severity Rating Scale (C-SSRS).
  - 21. Subject has any planned elective surgery due to occur during the study dosing period which in the opinion of the investigator could interfere with study procedures.
  - 22. Subject has a history of known inflammatory bowel disease, active diverticular disease, or a history of confirmed duodenal, gastric, or esophageal ulceration in the past 6 months.

#### **6.2.4        Exclusion criteria related to the IMP/concomitant medications/procedures**

- 23. Subject has a known hypersensitivity to any components of the IMP.
- 24. Subject has a history of hyperprolinemia, since L-proline is a constituent of rozanolixizumab.
- 25. Subject has received a live vaccination within 8 weeks prior to the Baseline Visit; or intends to have a live vaccination during the course of the study or within 7 weeks following the final dose of IMP.
- 26. Subject has received any experimental biological agent within or outside of a clinical study in the past 3 months or within 5 half-lives prior to Baseline (whichever is longer) (refer to [Table 6-1](#)).
- 27. Subject has had prior treatment with rituximab, ofatumumab, or ocrelizumab in the 6 months prior to the Baseline Visit or subject has had prior treatment with rituximab, ofatumumab, or ocrelizumab in the 12 months prior to Baseline and B cells are not within the normal range.
- 28. Subject has been treated with immunosuppressants, biologics, and other therapies in the recent timeframe as detailed in [Table 6-1](#) OR has been on permitted medications detailed in [Table 7-3](#), but has not been on stable dosing regimens of those medications as detailed in [Table 7-3](#).

**Table 6-1: Time restrictions required prior to Randomization Visit (Visit 2) for immunosuppressants, biologics and other therapies**

Generic name	Time restrictions required prior to Randomization Visit (regardless of route)
Immunosuppressants	
Cyclophosphamide	
Pimecrolimus	
Vinca alkaloids (vincristine, vinblastine)	
Biologics (mabs and fusion proteins)	
Abatacept (CTLA 4-Ig)	
Belimumab	
Golimumab	
Natalizumab	
Ofatumumab	
Rituximab	
Ocrelizumab	
Atacicept (TACI-Ig)	
Veltuzumab	
Other biologics	
Others	
Rigerimod	
PLEX	

CTLA 4-Ig=cytotoxic T lymphocyte-associated molecule-4 immunoglobulin; mabs=monoclonal antibodies; PLEX=plasma exchange; TACI-Ig=transmembrane activator and calcium modulator and cyclophilin ligand interactor-immunoglobulin

Note: For other immunotherapies not included in the table, consult with Medical Monitor prior to enrollment.

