## 6.4 Withdrawal criteria

Subjects are free to withdraw from the study at any time, without prejudice to their continued care.

Subjects **MUST be withdrawn from the study** if any of the following events occur:

1. Subject withdraws his/her consent.
2. Subject becomes pregnant during the study, as confirmed by a positive pregnancy test.

Subjects **must discontinue IMP** if any of the following events occur:

1. Subject develops an illness that would interfere with his/her continued participation.
- Subject has a serious infective episode requiring hospitalization or iv antibiotic therapy (including but not limited to bacteremia or sepsis, bacterial meningitis, osteomyelitis or septic arthritis, bacterial pneumonia, or visceral abscess).
- Subject has an AE of severe infusion reaction requiring corticosteroid and/or epinephrine therapy (see Section 12.1.9).
- Subject has an AE of severe anaphylactic reaction requiring corticosteroid and/or epinephrine therapy.
- Subject has a TB test that is confirmed positive or any further evidence suggestive of potential TB infection (eg, exposure) and further examinations result in a diagnosis of active TB or LTBI (refer to Section 12.3.7 for further details and instructions).
- If a nontuberculosis mycobacterium infection (NTMBI) is identified during a study, the same withdrawal procedures as those used for an active TB infection identified during the study should be followed.
2. Subject has active suicidal ideation as indicated by a positive response (Yes) to either Question 4 or Question 5 of the “Since Last Visit” version of the C-SSRS. The subject should be referred immediately to a Mental Healthcare Professional.
3. The sponsor or a regulatory agency requests withdrawal of the subject.
4. Subject needs or takes PLEX, dexamethasone or rituximab.
5. Subject is treated with rescue medication and/or relapses during the Treatment Period (refer to Section 7.7.3).

Subjects **may be discontinued from IMP** at the discretion of the investigator, Medical Monitor, and Study Physician if any of the following events occur:

1. Subject takes prohibited concomitant medications during the Treatment Period as defined in this protocol (refer to Section 7.7.2).

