### 7.7.2 Prohibited concomitant treatments (medications and therapies)

The following medications are prohibited during the Treatment Period:

- IVIg and SC Ig (refer to Section 7.7.3)
- All biologics including rituximab
- Cyclophosphamide
- Pimecrolimus
- IPP-201101 (LupuzorTM)
- PLEX
- IA
- Systemic dexamethasone

If a subject requires or takes IVIg, SC Ig, PLEX, dexamethasone, or rituximab they must be discontinued from IMP. In all other cases of intake of prohibited concomitant medication, the investigator will (where possible) discuss with the Medical Monitor and/or Sponsor Study Physician and a decision will be made whether the subject should discontinue IMP (see Section 6.4).

If a subject is discontinued from IMP they should be encouraged to complete Visit 17/PEOT and complete the Observation Period (see [Table 5–1](#) and Section [6.4](#)).

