### **8.1.1 Screening Visit 1 (Day -35 to Day -14)**

The following procedures will be performed at the Screening Visit (or as close as possible to the Screening date):

- Informed consent process including obtaining written informed consent from the subject
- iRODS assessment – to be performed before any other assessment after the consenting process
- Query for suicidality (C-SSRS)
- Tuberculosis Signs and Symptoms questionnaire
- Obtain a chest radiograph, unless one has been obtained 3 months prior to the Screening Visit
- Record subject demographics
- Verify (to the extent possible with available Screening Visit 1 information) that subject fulfills all the inclusion criteria and none of the exclusion criteria
- General medical and procedures history
- Prior medication
- Concomitant medical procedures
- CIDP history (symptoms, date of onset, therapy)
- Vital signs (taken once during the visit)
- Body weight (Screening weight will be used for calculation of the dose) and height
- 12-lead ECG
- Full physical examination
- Full neurological examination
- Recording of AEs

- Contact IRT
- Blood sample (the laboratory manual will provide guidance on the order of sample collection) for:
  - Clinical laboratory tests (ie, hematology, clinical chemistry, serology [including hepatitis C and hepatitis B virus-antibodies, human immunodeficiency virus 1 (HIV1) and human immunodeficiency virus 2 antibodies (HIV2)], and interferon gamma release assay [IGRA] for active and latent tuberculosis [LTB])
  - Serum pregnancy test for women of childbearing potential
  - Immunoglobulins (total IgG, IgG subclasses)
  - Vaccination-specific antibody titers (██████████)
  - ██████████
- Urine sample for urinalysis
- INCAT assessment
- RT-MRC assessment
- Assessment of grip strength by the site personnel
- Issue subject e-diary for daily record of grip strength
- Provide an appointment to the next visits (see Section 8.2 for details related to scheduling of the next visit)

At the end of the Screening Visit, subjects will be issued a subject e-diary in which they will record daily grip strength from the Screening Visit until the end of study participation. Subjects should be reminded to bring their diaries with them to each clinic visit and to have them available at home nursing visits.

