### **8.2.1           Visit 2 (Day 1, Baseline)**

The following procedures and assessments will be performed at Visit 2 (Day 1, Baseline):

- PROs should be conducted as the first assessments in the study in the following order:
  - iRODS assessment – to be performed before any other assessment
  - CIDP PRO instrument
  - Fatigue scale
  - PGIS
  - Query for suicidality (predose)
- Verification of inclusion/exclusion criteria (including results of laboratory samples, ECG, chest x-ray performed since Visit 1).
- Assessment of withdrawal criteria (see Section 6.4)
- Prior and concomitant medication
- Concomitant medical procedures
- Vital signs (taken predose, at the end of the infusion, at 2 hours and at 4 hours after the end of the infusion)
- Body weight (predose)

- 12-lead ECG (predose)
- Recording of AEs
- Brief physical examination (predose)
- Brief neurological examination (predose)
- Contact IRT and randomize the subject (upon confirmation of eligibility)
- Administration of IMP
- Urine sample for urinalysis (predose)
- Urine pregnancy test for women of childbearing potential (which must be confirmed negative prior to subject dosing)
- Blood sample (all samples should be taken predose unless otherwise specified; the laboratory manual will provide guidance on the order of sample collection) for:
  - Serum complement (C3, C4) and plasma complement (C3a, C5a)
  - Clinical laboratory tests (ie, hematology, clinical chemistry)
  - Serum cytokines
  - Immunoglobulins (total IgG, IgG subclasses)
  - Neurofilament light chain
  - Exploratory biomarker samples
  - RNA samples
  - CIDP-specific auto-antibodies
  - IgA, IgM, IgE
  - Whole blood for exploratory genetic (DNA)
  - PK of rozanolixizumab (predose and 4 hours postdose)
  - [REDACTED]
- INCAT assessment (predose)
- RT-MRC assessment (predose)
- Assessment of grip strength by site personnel (predose)
- Review subject e-diary for daily assessment of grip strength

Subjects should be reminded to continue to record daily grip strength in their diaries and to bring their e-diary with them to their next study visit.

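### Live vaccination is barred only as an intention held at entry: neither Protocol 7.7.2 nor 6.4 prohibits a live vaccine once a participant is in the study

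*Protocol*

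**What the plan says.** **Entry rule.** Protocol 6.2.4, Exclusion 25, excludes a subject who had a live vaccine in the 8 weeks before Baseline, or who "intends to have a live vaccination during the course of the study or within 7 weeks following the final dose of IMP". The forward-looking part has two limbs: the course of the study, and 7 weeks after the last dose.

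**When it is checked.** At Visit 1 (8.1.1) the site verifies, as far as the available information allows, "that subject fulfills all the inclusion criteria and none of the exclusion criteria". At Visit 2 (8.2.1) it repeats the check: "Verification of inclusion/exclusion criteria (including results of laboratory samples, ECG, chest x-ray performed since Visit 1". The schedule of assessments shows no later verification.

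**On-study prohibitions.** Section 7.7.2 opens with "The following medications are prohibited during the Treatment Period". It lists IVIg and SCIg, biologics, cyclophosphamide, pimecrolimus, IPP-201101, PLEX, IA and systemic dexamethasone. No vaccine is named. For listed items that do not force discontinuation it says "In all other cases of intake of prohibited concomitant medication, the investigator will (where possible) discuss with the Medical Monitor".

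**Withdrawal and discontinuation.** In 6.4 the mandatory IMP stops for treatment are "Subject needs or takes PLEX, dexamethasone or rituximab" and rescue medication. A discretionary stop applies if "Subject takes prohibited concomitant medications during the Treatment Period as defined in this protocol", with a reference to 7.7.2. A further 6.4 clause, under discretionary study withdrawal, sends prohibited medication other than the named drugs to a discussion about IMP. It has no reference to 7.7.2 and no limit to the Treatment Period.

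The remaining mentions of vaccines (Protocol 3.3, the schedule of assessments, the Section 8 blood samples, SAP 2.1.3) concern antibody levels. None restricts vaccination.

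**The concern.** The sponsor treats live vaccination as a risk throughout the study and for 7 weeks after dosing, but the protocol applies that judgement only to plans held at entry. Someone with no plan at Visits 1 and 2 may later be offered a live vaccine. A site that follows the prohibited list exactly would find nothing against it.

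The stake is participant safety. Section 5.4.4 expects maximum mean IgG reductions above 70% over the Treatment Period in the active arm, about 17 of the 34 participants. The site cannot tell who they are, because 7.8.1.1 withholds results that could unblind. Table 7-3 also permits background immunosuppressants in both arms, including prednisolone up to 30 mg/day, methotrexate, mycophenolate and azathioprine. A rule would have to cover everyone.

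**Working it through.** There is no plan figure to reproduce. The check compares the relevant sections and then works out which days each covers.

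**Does any on-study text prohibit a live vaccine?**

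| Text | Reaches a live vaccine? |
|---|---|
| Exclusion 25 | Only as receipt before Baseline or intention at entry |
| 7.7.2, named items | No vaccine item |
| 7.7.2, biologics item | Unlikely: Table 6-1 glosses the class as monoclonal antibodies and fusion proteins. On a wider reading the ban would still end with the Treatment Period |
| 6.4, mandatory stops | No |
| 6.4, discretionary stop | Depends on 7.7.2 |
| 6.4, further prohibited-medication clause | Acts only on something already prohibited, and 7.7.2 is the only list of what is prohibited |
| 6.4, noncompliance and sponsor request | General discretion; neither forbids a vaccine |
| 6.4, serious infective episode | Acts on a consequence, after exposure |
| Concomitant medication at each visit | Detects an exposure, does not prevent it |

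**Which days does Exclusion 25 span?** Inputs: first dose Day 1; last scheduled dose Day 78 (Visit 16); Visit 17 Day 85; Final Visit 12 weeks after the last dose; stabilization up to 24 weeks after the last dose (5.1, 5.1.1, 8.3, 8.4).

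- 7-week limb: 7 × 7 = 49 days. Full dosing: 78 + 49 = Day 127 (Day 125 to 129 with the ±2-day visit window).
- Study limb, full dosing: 78 + 12 × 7 = Day 162. This is 162 − 127 = 35 days beyond the 7-week limb.
- Study limb with the longest stabilization: 78 + 24 × 7 = 78 + 168 = Day 246.
- Only the Day 1 dose given: 7-week limb 1 + 49 = Day 50; scheduled Final Visit 1 + 84 = Day 85.
- Entry to CIDP04 at Visit 17: CIDP01 participation ends at Day 85, so 127 − 85 = 42 of the 49 post-dose days fall under a protocol that is not supplied.

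The study limb is normally the longer one. The 7-week limb is longer for immediate CIDP04 entrants and for anyone who leaves within 7 weeks of the last dose.

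**What does the 7.7.2 heading cover?** The Treatment Period runs from first to last dose, Day 1 to Day 78 with full dosing. A vaccine item simply added under that heading would still leave Day 79 to Day 162 without a rule.

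**The case against.** The strongest reply is that the residual risk is small and partly controlled. Intention is screened twice. Inclusion 2 requires a participant judged reliable. Concomitant medication is recorded throughout, and 6.4 leaves the investigator and sponsor discretion. An instruction may also sit in the consent form, the Investigator's Brochure or the Protocol Deviation Specification. Most of this stands and limits the point to a minor one. It does not supply a prohibition in the protocol.

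Three stronger readings are tempting but unsupported.

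- A reader might infer that Exclusion 25 is an outlier among exclusions that are otherwise carried on-study. Some are carried: pregnancy has "Subject becomes pregnant during the study, as confirmed by a positive pregnancy test" in 6.4, TB and suicidality have criteria there, and rituximab appears in both 7.7.2 and 6.4. Others have no specific counterpart: planned elective surgery (Exclusion 21, also plan-based), HbA1c above 6.0% (3), neoplasia (19) and the vinca alkaloids in Table 6-1. The case rests on the sponsor's own post-dose window, not on uniqueness.
- A reader might infer that every medication clause in 6.4 leads back to 7.7.2. One does not, as set out above. It still needs the medication to be prohibited first.
- A reader might infer that the exposed window closes 7 weeks after dosing. That drops the first limb of Exclusion 25.

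**Conclusion.** The gap is real and small. The protocol contains no explicit on-study prohibition of live vaccines, although its entry criterion shows that the sponsor regards them as a risk for the whole study and at least 7 weeks after the last dose. It concerns only participants whose plans change after Visit 2. The documents give no frequency; few are likely to be affected. With full dosing the span without a rule is Day 1 to Day 162, up to about Day 246 with the longest stabilization, or to Day 127 (partly under CIDP04) for those who move across at Visit 17.

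The conclusion rests on the narrow reading of biologics for the dosing period; the post-dose gap does not depend on it. It takes the sponsor's 7-week margin as given, because the documents do not state how long IgG stays suppressed after the last dose. It is limited to the protocol and SAP: a reader might infer that participants receive no instruction at all, and that cannot be concluded from these two documents. The estimand, analysis and sample size are unaffected.

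**What to change.** Add a separately worded provision to 7.7.2, outside the Treatment Period heading. It should prohibit live vaccines from the first dose until the end of study participation or 7 weeks after the final dose, whichever is later. This matches both limbs of Exclusion 25. Refer any exposure during dosing to the Medical Monitor for a decision on IMP, using the route that 7.7.2 and 6.4 already provide. Confirm that CIDP04 carries an equivalent rule for participants who enter at Visit 17.

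The cost is a short amendment with the approvals that 15.5 requires; it can be bundled with the next one. No new procedure is needed while a participant is in CIDP01, because concomitant medication is already recorded at Visits 17 to 21 and at stabilization visits (8.3.1 to 8.3.3). The downside is that participants could not have an elective live vaccination during follow-up. Label: cheap improvement, minor safety.
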